7.3.2 Secondary endpoint analyses

If considered necessary an MCPMod approach will also be applied to selected secondary endpoints.

Comparisons between treatment groups will be exploratory in nature and based on the numerical comparison of the respective response rates. In addition, unadjusted absolute risk differences of the response rates at week 52 between the BI 655064 arms and the placebo group will be analysed. The proportion of responders in each arm, the risk difference between each arm and placebo and 95% exact confidence intervals will be displayed.

Further details will be given in the TSAP.

7.3.4 Safety analyses

All treated patients will be included in the safety analysis. In general, safety analyses will be descriptive in nature and will be based on BI standards. No hypothesis testing is planned.

Adverse events will be coded using the Medical Dictionary for Regulatory Activities (MedDRA) coding dictionary. Standard BI summary tables and listings will be produced. All adverse events with an onset between start of treatment and end of the residual effect period (REP), a period of 50 days after the last dose of trial medication, will be assigned to the treatment period for evaluation. Analysis will be performed based on randomised treatment.

Statistical analysis and reporting of adverse events will concentrate on treatment-emergent adverse events. To this end, all adverse events occurring between start of treatment and end of the residual effect period will be considered 'treatment-emergent'. The residual effect period is defined as 50 days. Adverse events that start before first drug intake and deteriorate under treatment will also be considered as 'treatment-emergent'.

Frequency, severity, and causal relationship of adverse events will be tabulated by system organ class and preferred term after coding according to the current version of the Medical Dictionary for Drug Regulatory Activities (MedDRA).

Laboratory data will be analysed both quantitatively as well as qualitatively. The latter will be done via comparison of laboratory data to their reference ranges. Values outside the reference range as well as values defined as clinically relevant will be highlighted in the

listings. Treatment groups will be compared descriptively with regard to distribution parameters as well as with regard to frequency and percentage of patients with abnormal values or clinically relevant abnormal values.

Vital signs, physical examinations, or other safety-relevant data observed at screening, baseline, during the course of the trial and at the end-of-trial evaluation will be assessed with regard to possible changes compared to findings before start of treatment.

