6. GENERAL ANALYSIS DEFINITIONS

6.1 TREATMENTS

For reporting purposes, all randomised patients will be classified into one of the following treatment groups:

Sort order	Treatment	Long label	Short label
01	B	BI 655064 120mg	BI 120mg
02	C	BI 655064 180mg	BI 180mg
03	D	BI 655064 240mg	BI 240mg
04	A	Placebo	Placebo

These will be the default labels and sort order for reporting the treatment groups.

The following study periods based on actual start and stop dates of study treatment administration are defined:

Screening: day of informed consent to day prior to the start of randomised medication

Treatment: start date of randomised double-blind medication to date of last dose

Follow-up: day after the last dose of randomised double-blind medication through trial completion and after trial completion

Rules for assigning AEs/laboratory data to the study periods are as follows.

AEs/laboratory data will be assigned to the treatment period if they occur/samples were taken after the first injection of study medication to the date of last administration of study medication plus 50 days.

Since AE onset time was not recorded, investigators were asked to provide more information for AEs with date of onset equal to date of first injection. Additional information was to be provided in the AE comment field. The trial team will review the comments & will impute a time to capture onset as prior to or following first injection of study medication. An analysis data set will be created to incorporate this information. If the site indicates that the AE onset time is prior to trial medication administration then the AE will be assigned to the screening period. If the site indicates that the AE onset time is after trial medication administration or there is no information regarding onset then the AE will be assigned to the treatment period.

Adverse events with onset on or after the 51st day after the last administration of trial medication will be considered 'Follow-up' events. However, if the patient rolls over to the extension trial (1293.13) & receives the first dose of trial medication in 1293.13, any new events or worsening of existing events will be assigned to the treatment period of 1293.13.

Laboratory data on or after the 51st day after the last administration of trial medication will be considered 'Follow-up' data.

Proprietary confidential information © 2020 Boehringer Ingelheim International GmbH or one or more of its affiliated companies

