6.2 IMPORTANT PROTOCOL DEVIATIONS

The following table defines the different categories of important protocol deviations (iPDs). The final column indicates which iPDs will be used to exclude patients from the different patient analysis sets.

Patients with iPDs will be documented. The following list of iPDs will be used; note that this is a working list and may not be finalised until the final Report Planning Meeting (RPM) prior to database lock.

Excluded from ‘None’ denotes a safety iPD.

Table 6.2: 1 Handling of iPDs

Category/ Code	Description	Example/Comment	Excluded from
A	Entrance criteria not met		
A1.1	Inclusion criteria 3, 4 or 5 not met	Inclusion criteria, 3, 4 (including biopsy class, active or active/chronic disease and time between biopsy & screening) or 5 not met as specified in the protocol (automatic PD)	PPS
A1.2	Inclusion criteria 1 not met	Inclusion criteria 1 not met as specified in the protocol (automatic PD)	None
A2	Exclusion criteria 2, 3, 4, 7, 10-12 met*	Exclusion criteria 2, 3 [4], 4 [5], 7 [8B], 10 [11], 11 [12A or 12B], 12 [13] met as specified in the protocol (automatic PD)	PPS/ (TBD at MQRM/ BRPM)
B	Informed consent		
B1	Informed consent not available/not done	Informed consent date missing (automatic PD)	All
B2	Informed consent too late	Informed consent date <actual consent date> was after Visit 1 date <Visit 1 date> (automatic PD)	None
C	Trial medication and randomization		
C1	Randomization not followed	Patient not treated according to randomization.	PPS/ (TBD at MQRM/ BRPM)
C2	Wrong dosage schedule	Wrong dose of BI 665064 taken or syringes used in the wrong order	PPS/ (TBD at MQRM/ BRPM)
C3	Non-compliance with study medication	Any evidence of gross non-compliance (manual or automatic PD) as defined in Section 5.4 . iPDs were not assigned if a patient had documented reasons for non-compliance such as AE (which was allowed per protocol) or drug not at site.	PPS/ (TBD at MQRM/ BRPM)

Proprietary confidential information © 2020 Boehringer Ingelheim International GmbH or one or more of its affiliated companies

Table 6.2: 1 (continued) Handling of iPDs

Category/ Code	Description	Example/Comment	Excluded from
C4	Medication code broken inappropriately	Medication code broken inappropriately - reason for medication code break <reason> (manual PD)	PPS
D	Concomitant medication		

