6.3 SUBJECT SETS ANALYSED

- **Randomised set:**
This patient set includes all randomised patients, whether treated or not.
- **Treated set:**
This patient set includes all patients who were dispensed study medication and were documented to have taken at least one dose of investigational treatment.
- **Intent to treat (ITT) set:**
This patient set includes all patients from the treated set who have a baseline (or screening) proteinuria (spot urine can be used if patient does not have 24-hour collections) and baseline or screening eGFR
- **Per protocol set (PPS):**
This patient set includes all patients in the ITT who completed at least 46 weeks of the treatment regimen and do not have iPDs leading to exclusion from the PPS as defined in [Table 6.2: 1](#)

Table 6.3: 1 Subject sets analysed

Class of endpoint	Patient set		
	Treated set	ITT	PPS
Primary endpoint: CRR at week 52		X (primary analysis)	X
Secondary endpoints		X	X
Safety endpoints	X		
Demographic/baseline endpoints	X		

Note that the number of patients with available data may differ across endpoints. For details, see [Section 6.6](#) “Handling of missing data”.

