7.8 SAFETY ANALYSIS

All safety analyses will be performed on the treated set and performed in accordance with BI standards. Tabulations of frequencies/proportions will be used for the evaluation of categorical (qualitative) data, and tabulations of descriptive statistics will be used to analyse continuous (quantitative) data.

The format of the listings and tables will follow the BI guideline ‘Reporting of clinical trials and project summaries’ (6).

The individual values of all subjects will be listed, sorted by treatment, subject number and visit. The listings will be contained in Appendix 16.2.

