7.8.1 Adverse events

AEs will be analysed using BI standards, as described in the guideline, ‘Handling and summarization of adverse event data for clinical trial reports and integrated summaries’ (7).

Unless otherwise specified, the analyses of adverse events will be descriptive in nature. All analyses of AEs will be based on the number of patients with AEs and NOT on the number of AEs.

The analysis of AEs will be based on the concept of treatment emergent AEs. This means that all AEs occurring between first drug intake and end of the residual effect period (REP) will be assigned to the randomised treatment. The residual effect period is defined as 50 days. All AEs occurring before first drug intake will be assigned to ‘Screening’ and all AEs occurring after last drug intake + 50 days will be assigned to ‘Follow-up’ (and presented in listings only). For details on the treatment definition, see [Section 6.1](#)

According to ICH E3 (8), in addition to Deaths and Serious Adverse Events, ‘other significant’ AEs need to be listed in the clinical trial report. These will be any non-serious adverse event that led to an action taken with study drug (e.g. discontinuation or dose reduced or interrupted).

An overall summary of adverse events will be presented. The frequency of patients with adverse events will be summarised by treatment, primary system organ class and preferred term. Separate tables will be provided for patients with adverse events leading to treatment discontinuation, other significant adverse events according to ICH E3 (8), related adverse events and serious adverse events. AEs will also be summarised by maximum RCTC grade.

Proprietary confidential information © 2020 Boehringer Ingelheim International GmbH or one or more of its affiliated companies

Adverse events of special interest (AESI) will be presented in tables and listings for the following:

- Injection site reactions and hypersensitivity, including anaphylaxis reaction
- Malignancies, lymphoproliferative disorders
- Severe infections and opportunistic infections
- Thromboembolism (Thrombosis and adjunct immunosuppression)
- Cytokine release syndrome
- Drug induced liver injury (DILI) (if applicable)

The system organ classes will be sorted by frequency, PTs will be sorted by frequency (within SOC).

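### Safety is tabulated by randomised arm, so a patient who took another arm's regimen for most of the trial has adverse events counted under a treatment not taken

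*Protocol*

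**What the plan says.** Protocol 7.3.4 defines the safety population by exposure: "All treated patients will be included in the safety analysis". It then fixes the grouping: "Analysis will be performed based on randomised treatment".

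The SAP has the same structure. Section 7.8 sets the population: "All safety analyses will be performed on the treated set and performed in accordance with BI standards". Section 6.3 defines that set as patients who were dispensed medication and "were documented to have taken at least one dose of investigational treatment". This decides who is included, not the arm in which they are counted. Section 7.8.1 says that events from first drug intake to the end of the 50-day residual effect period "will be assigned to the randomised treatment". Section 6.1 opens with "For reporting purposes, all randomised patients will be classified into one of the following treatment groups" and lists the three dose groups and placebo. It uses actual start and stop dates to define study periods, but has no rule that places a patient in the arm actually received.

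SAP Table 6.2: 1 foresees departures from the assigned treatment. C1 is described as "Patient not treated according to randomization" and C2 as "Wrong dose of BI 665064 taken or syringes used in the wrong order". The consequence listed for each is exclusion from the per protocol set, still to be settled at a review meeting. SAP Table 6.3: 1 uses that set for the primary and secondary endpoints and not for safety.

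**The concern.** A safety table is meant to show what happened to patients exposed to a given regimen. Grouping by randomised arm does this only as long as patients took what they were randomised to. When a patient took another arm's regimen throughout, the plan as written credits the events to the wrong regimen. On average such errors draw the arms together, and they can make an event on active drug look like a placebo event.

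This trial is more sensitive to such an error than most. Protocol 7.1 makes choice of dose on efficacy and safety the primary objective, and Protocol 7.3.1 brings safety information into the choice of target dose. Safety is purely descriptive, so the counts by arm are the evidence. Two arms have about 20 patients. For rare events of special interest, such as thrombosis or lymphoproliferative disorder, one case in one arm or another can change how a dose is read.

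**Working it through.** The plan states no figure on this point, so there is none to reproduce. The check has a reading part and a scale part.

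**Reading**

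- Protocol 7.3.4: all treated patients, grouped as randomised.
- SAP 7.8.1: treatment-emergent events go to the randomised treatment.
- SAP 6.1 and 6.3: reporting groups and the treated set, with no rule for treatment received.
- SAP 6.2: C1 and C2 recognised, with a consequence for the per protocol set only.
- SAP section 4 (changes to the planned analysis): no change to the safety grouping.

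The randomised grouping therefore stands, and no analysis by treatment received appears in the available text.

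**Scale: one arm**

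Arm sizes from Protocol 7.6: placebo 40, 120 mg 20, 180 mg 20, 240 mg 40 (40 + 20 + 20 + 40 = 120).

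If k patients of an arm of n have the event, taking out one affected patient changes the rate by k/n − (k − 1)/(n − 1) = (n − k)/[n(n − 1)]. This is largest at k = 1, where it equals 1/n:

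- n = 20: 1/20 = 5.0 points.
- n = 40: 1/40 = 2.5 points.

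These are ceilings. For a common event the shift is smaller: 10/20 becomes 9/19, which is 50.0% − 47.4% = 2.6 points; 16/20 becomes 15/19, which is 80.0% − 78.9% = 1.1 points.

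**Scale: difference between two arms**

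Illustration with assumed counts: one patient with an event is randomised to placebo but takes the 120 mg regimen throughout. The columns show the 120 mg minus placebo difference.

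| Other events (placebo, 120 mg) | By randomised arm | By treatment received | Shift |
|---|---|---|---|
| 0, 0 | 0/20 − 1/40 = −2.5 | 1/21 − 0/39 = +4.8 | 7.3 |
| 2, 1 (about 5%) | 1/20 − 3/40 = −2.5 | 2/21 − 2/39 = +4.4 | 6.9 |
| 4, 2 (about 10%) | 2/20 − 5/40 = −2.5 | 3/21 − 4/39 = +4.0 | 6.5 |

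The difference moves by more than either arm's rate because the patient leaves one arm and enters the other. In this illustration the sign changes.

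**How likely is it?**

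The documents give no misallocation rate. Under an assumed per-patient probability p, the chance of at least one such patient among 120 is 1 − (1 − p)^120: 45% at p = 0.5%, 70% at 1% and 91% at 2%. These figures depend entirely on p and are not evidence that it happened.

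**Which C2 cases matter?**

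Protocol Table 4.1.4: 1 gives 2 syringes in each of weeks 0 to 2 and 1 in each of weeks 3 to 51, so 3 × 2 + 49 = 55 syringes per patient. In the 120 mg and 180 mg arms, active and placebo syringes alternate from week 3. Swapped order or one wrong syringe out of 55 leaves the patient on essentially the assigned regimen. Only C1 cases and sustained wrong dosing put a patient on another arm's regimen.

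**The case against.** The strongest case on the other side has five parts.

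1. **The effect is hypothetical.** No misallocated patient is reported. The interactive response system assigns medication numbers for each weekly administration, and compliance is checked at each clinic visit from Visit 4. This stands: a reader might infer that events have been, or will be, misattributed, and the documents do not support that.

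2. **Most dosing errors do not change the arm.** A reader might infer that events of any wrongly dosed patient are miscounted. That goes too far, because most of what C2 covers would leave the patient in the same arm under either grouping.

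3. **The SAP phrase may concern periods.** SAP 7.8.1 contrasts the randomised treatment with screening and follow-up and refers to section 6.1, so it can be read as allocating events to a study period. Taken alone, the phrase allows that reading. It does not remove the protocol's sentence, which is explicit about grouping. The company standards cited in SAP 7.8 and 7.8.1 may hold an as-received convention, but they are not available here.

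4. **The patients can be traced.** A reader might infer that C1 and C2 serve no purpose beyond the per protocol set. SAP 6.2 says that patients with important deviations will be documented, calls the table a working list, and leaves exclusion to a meeting. Individual data are listed by treatment, subject and visit. A careful reader could match a C1 patient to the events. This stands, but the summary tables by arm would still be wrong for that patient, and no listing showing both treatments is promised.

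5. **Grouping as randomised is pre-specified, keeps the randomised comparison, and feeds no hypothesis test.** This is true and limits the consequence. It does not make the randomised arm a correct label for exposure in a safety table.

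**Conclusion.** The point holds in a narrow form. Followed as written, the plan reports the adverse events of a patient who took another arm's regimen for all or most of the trial under a treatment that the patient did not take. One such patient with an event moves an arm's rate by at most about 5 points (n = 20) or 2.5 points (n = 40), and by less when the event is common. A difference between two arms can move further: 6.5 to 7.3 points in the placebo-to-120 mg illustration. If no patient is misallocated, nothing changes.

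The conclusion rests on the planned arm sizes and on the unseen company standards not overriding the protocol's sentence. The event counts and misallocation rates used above are assumptions. The two documents do not contradict each other. The rule they share is a poor choice for a contingency that the SAP itself foresees. It is a minor improvement, worth making because it is cheap and safety by dose informs dose selection.

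**What to change.** In Protocol 7.3.4 and SAP 6.1, 7.8 and 7.8.1, state that safety on the treated set is summarised by treatment actually received, as follows:

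- A patient is counted in another arm only if that arm's regimen was received for all or most of the treatment period. The SAP should define most, for instance as more than half of the weekly administrations.
- Patients with isolated wrong syringes or order errors stay in their randomised arm. So do patients whose exposure matches none of the four regimens.
- The rule is fixed, and individual cases are decided, before database lock by someone who does not see the outcome data. Protocol 4.1.5.1 keeps allocation from the trial team until lock, so this person should be outside the team.
- Adverse events of C1 and C2 patients are listed with randomised and received treatment side by side.

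A rule based on the highest active dose received should not be used. The 120 mg and 240 mg arms use the same 120 mg syringe and differ in number and frequency of injections, so one syringe does not identify an arm. Such a rule would also move a placebo patient into an active group after one stray injection.

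The cost is an actual-treatment variable derived from the interactive response system and drug accountability records, plus the wording. The safety grouping may differ slightly from the efficacy grouping, which a table footnote can explain. Efficacy analyses do not change.

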7.4 INTERIM ANALYSES

An interim analysis via an internal but independent team will be performed after all patients, complete 26 weeks of treatment. Alpha adjustments will not be made due to the exploratory nature of the assessment. At that timepoint, a preliminary database lock will be performed.

The independent team will review all available unblinded safety, efficacy and This review is for internal planning purposes to facilitate further substance development. An interim analysis trial statistical plan will be written to define which functions will have access to the unblinded data.

7.5 HANDLING OF MISSING DATA

As an imputation technique to deal with the missing data in this study, for the analysis of primary and secondary endpoints, non-completers considered failure (NCF) will be used. All other endpoints will be analysed without imputing for any missing data.

7.6 RANDOMISATION

An IRT will be used for the assignment of subjects to treatment groups. Randomisation will be done with stratification by ethnicity (Asians vs Non-Asian) and proteinuria at screening (<3g/day or ≥ 3g/day (respectively UP/UC<3 or UP/UC≥3))

. The influence of covariates (in particular with regard to Hispanics and Black / African-Americans) will be analyzed in a sensitivity analyses.

Patients will be randomized in blocks to double-blind treatment. Patients will be randomized to placebo and each treatment group in the following ratio 2:1:1:2 (approx. 40 patients allocated to placebo and 240mg, approx. 20 patients each to 120mg and 180mg). BI will arrange for the randomization and the packaging and labelling of trial medication. The randomization list will be generated using a validated system, which involves a pseudo-random number generator so that the resulting treatment will be both reproducible and non-predictable. The block size will be documented in the CTR. Access to the codes will be controlled and documented.

7.7 DETERMINATION OF SAMPLE SIZE

The aims of this study are two-fold. A first aim is to show a significant non-flat dose-response curve across the different doses and placebo. Additionally to that at least one modelled dose within the dose range considered [0mg, 240mg] should show a benefit of at least 10% compared to placebo.

Assumptions for the efficacy of the different doses are provided in the table below.

Based on these assumptions and the planned sample size of 120 (=40:20:20:40) the success probability is approximately 82% for the base case of approximately 20% treatment benefit compared to placebo (45% vs 25% complete renal response rate at week 52). In case that there is only a minor treatment benefit the false success probability is basically limited by the α -level for the significance testing of the non-flat dose-response curve that is 20%.

Table 7.7:1: Success probabilities under different efficacy assumptions

Dose/ Scenario	0	120	180	240	Max. Effect	Sample Size	Alpha	Delta	Simulated power
Expected A	0.25	0.30	0.38	0.44	0.45	40:20:20:40	20%	10%	82%
Expected B	0.25	0.30	0.38	0.44	0.45	35:35:35:35	20%	10%	81%
Type I	0.25	0.255	0.26	0.265	0.27	40:20:20:40	20%	10%	21%
Shift	0.45	0.5	0.58	0.64	0.65	40:20:20:40	20%	10%	80%
Bad	0.25	0.275	0.30	0.34	0.35	40:20:20:40	20%	10%	49%
Type I Shift	0.45	0.455	0.46	0.465	0.47	40:20:20:40	20%	10%	22%

Success probabilities under different efficacy assumptions for the defined success criteria of 1) Significant non-flat dose-response AND 2) Treatment benefit of at least delta compared to placebo for at least one modelled dose within the considered dose range

Scenarios considered:

- Expected A: Main scenario reflecting assumptions for efficacy of 25% (placebo), 30% (low dose), 38% (medium dose), 44% (high dose) and 45% (maximum efficacy). Sample size considered is 40:20:20:40=120 patients with a 2:1:1:2 allocation.
- Expected B: Same scenario as A but for equal allocation and a larger sample size of 140 total. Shows that 'Expected A' (unequal allocation) with 120 patients provides approximately the same success probability with 120 patients as 'Expected B' (equal allocation) with 140 patients.
- Type I: Scenario reflecting almost no treatment benefit. Difference between maximum efficacy and placebo is 2% only (27%-25%). Shows that error probability is approx. 20% in such a case which is driven by the alpha for dose-response curve testing.
- Shift: Same benefit of treatment to placebo in efficacy but with a shift of 20% in all assumed response rates. Shows that success probability is robust if actual response rates are quite different from 'guesstimates' given by 'Expected A' scenario.
- Type 1 Shift: Shift scenario for very small treatment benefit of 2% only. Shows that still alpha drives error probability if actual response rates are quite different from 'guesstimates'.
- Bad: Scenario with a low treatment benefit of 10% maximum compared to placebo. Represents a 'worse-case' scenario of treatment where treatment benefit is in a region where it is borderline efficacious.

Calculations were performed using R version 3.1.3.

